#### 6.2. Secondary Endpoints

## 6.2.1. Secondary Endpoint 1 - Proportion of CAP events by S pneumoniae serotypes

Distribution of *S. pneumoniae* serotypes identified by blood, high-quality respiratory cultures, or a serotype-specific UAD assay among the CAP population with culture and/or UAD1/2 testing are done, and among all CAP participants with a pneumococcus identified.

#### 6.2.1.1. Secondary Endpoint 1 - Main Analysis

We will calculate the proportion of participants infected with any of these 20 serotypes (1, 3, 4, 5, 6A, 6B, 7F, 9V, 14, 18C, 19A, 19F, 23F, 8, 10A, 11A, 12F, 15B, 22F, or 33F) as well as for each serotype among all CAP population 60 years or older having their culture and/or UAD test done with the 95% CIs for proportion. Groupings for PCV13 and PCV20 will be included.

The calculations will also be made among the *Sp*+ subpopulation that includes all CAP population in whom a pneumococcus identified by culture, UAD, or Binax.

The subgroup analysis will be done by risk status (high-risk, at-risk, and low-risk), age group (60-74 years,75-84 year and ≥85 years), and by COVID-19 status (COVID-19 positive and COVID-19 negative).

# 6.2.2. Secondary Endpoint 2 - Proportion of respiratory pneumococcal carriage among the CAP population

Proportion of CAP cases where the pneumococcal carriage is identified from saliva by culture or by PCR, divided by all CAP cases where the participants had a valid saliva specimen test result.

## 6.2.2.1. Secondary Endpoint 2 - Main Analysis

The numerator in this analysis will be the participants with pneumococcal carriage identified from saliva by culture or PCR by reference laboratory. The denominator will be the CAP population and who will have valid carriage results from the reference lab. We will calculate the proportion of participants with pneumococcal carriage of two target genes (lytA and piaB) detected from saliva among this population.

The calculations will also be made by risk status (high-risk, at-risk, and low-risk) and by age group (60-74 years, 75-84 years and ≥85 years).

# 6.2.3. Secondary Endpoint 3 - Proportion of participants having S. pneumoniae with underlying risk among the CAP population

Proportion of participants with a medical risk condition (at-risk and high-risk) among all CAP population as well as among participants with pneumococcus isolated from blood, high-quality respiratory cultures, a serotype-specific urinary antigen detection (UAD) assay or BinaxNow.

#### 6.2.3.1. Secondary Endpoint 3 - Main Analysis

The following calculations will be made, overall and by risk condition:

- Proportion of participants (with 95% CI for proportion) with at-risk medical condition among all CAP population
- Proportion of participants (with 95% CI for proportion) with high-risk medical condition among all CAP population

DMB02-GSOP-RF02 5.0 Statistical Analysis Plan Template 05-Dec-2019
PFIZER CONFIDENTIAL
Page 35
TMF Doc ID: 98.03

- Proportion of participants (with 95% CI for proportion) with at-risk medical condition among the Sp+ subpopulation
- Proportion of participants (with 95% CI for proportion) with high-risk medical condition among the Sp+ subpopulation

## 6.2.4. Secondary Endpoint 4 - Proportion of participants with an S. pneumoniae with antibiotic resistance

Proportion of S. pneumoniae isolates with antibiotic susceptibility identified by SOC testing, overall and by susceptibility type. Proportion with multidrug resistance will also be calculated.

## 6.2.4.1. Secondary Endpoint 4 - Main Analysis

The analysis will be conducted including participants Sp+ by culture (based on testing of isolates by reference lab or local lab) among all CAP population with information on antibiotic susceptibility results. If the antibiotic susceptibility data is missing or not done for a participant and for a drug, then the participant will be excluded from the analysis for that particular drug. For participants whose Sp isolates were tested for antibiotic susceptibility at the Reference Lab, the results of the Reference Lab will be used in the analysis rather than the local clinical laboratory results. For participants who are detected as Sp+ via culture method but without serotype information ('Not Serotyped'), the participants will also be included in the analysis if antibiotic susceptibility results are available from the reference lab or the local clinical lab.

The following drugs: Penicillin, Amoxicillin, Cefotaxime, Erythromycin, Clindamycin, Tetracycline, and Levofloxacin are included in the antimicrobial susceptibility test. The antibiotic susceptibility will be categorized as: Susceptible, Resistant, and Multidrug Resistant and the proportion of each of the categories for each of the drugs will be calculated.

#### 6.3. Other Endpoints

## 6.3.1. Exploratory Endpoint 1 – Rate of CAP events in the surveillance region

Incidence rates for hospitalized CAP and Sp+CAP (both overall and radiologically confirmed) obtained from screening log among individuals  $\geq 60$  years in surveillance region.

#### 6.3.1.1. Exploratory Endpoint 1 - Main Analysis

The incidence rate of CAP  $(IR_{CAP})$  will be calculated as

$$IR_{\textit{CAP}} = \frac{\textit{no. of CAP cases in the screening log} \div \textit{no. of years of surveillance}}{\textit{total population of the hospitals' geographical catchment area}} \times 100,000$$

The no. of years of surveillance will be calculated as

(date of last person 1st visit – date of the start of the surveillance period +1)/365.25

Note that the date of start of surveillance will be obtained from the Clinical Scientist of this study based on the data that it is confirmed that all pneumonia cases are being captured on the screening log.

DMB02-GSOP-RF02 5.0 Statistical Analysis Plan Template 05-Dec-2019
PFIZER CONFIDENTIAL
Page 36
TMF Doc ID: 98.03

We will compute distribution of the following variables between cases obtained from eCRF (enrolled patients) and Screening Log (not included in the eCRF/not enrolled) to evaluate the representativeness of the enrolled cases:

- Age
- Sex
- Nationality
- Radiologically confirmed CAP
- ICU Status

We will perform chi-square or Fisher's exact test, as appropriate, for the categorical variable and Student's T-test or Wilcoxon-Mann-Whitney test, as appropriate, for the continuous variables to evaluate the differences between the two populations (enrolled versus not enrolled).

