10. STUDY PROCEDURES

10.1. Surveillance Process

10.1.1. Surveillance Manual

The Surveillance Manual should describe and identify the following:

- Description of the informed consent process, including the staff roles responsible for informed consent.
- Description of the study-level Surveillance Officer role, which will be responsible for coordinating all enrolment activities at the participating sites. Additionally, site-level surveillance coordinators may be utilized.
- Identification of key personnel in each hospital that will assist with enrolment. This list should include the key posts at each ward who will serve as important sources of information for identification of inpatients with pneumonia. Ideally, numerous sub-investigators and site staff across various departments/wards will be involved to ensure constant and complete surveillance.
- Surveillance team structure, training and engagement should be addressed.
- Description of the process for sample collection.
- Establishment of communication and collaboration mechanisms between the surveillance staff and the local laboratory that will manage samples.

- Development of validated links with the testing laboratories for result reporting, if possible.
- Description of the laboratory testing procedures for SP, and methods for safe shipping and handling of the samples.
- A detailed step-by-step description of the screening process. This should include a description of how staff will be contacted to identify patients being admitted with pneumonia. This can also include how hospital admissions records, patient medical records, radiology reports and microbiology reports will be reviewed to identify patients being admitted with pneumonia.
- A step-by-step process of enrolment, including procedures used to identify patients being admitted with pneumonia, consent, enrolment, specimen collection, review of medical records of enrolled individuals, participant follow-up.
- The use of the screening and enrolment log, which will record all identified hospitalised patients admitted with pneumonia, whether or not they are eligible for the study, and whether or not the eligible individuals were enrolled.

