- Enrolment will ideally be within 24 hours of admission to the hospital on weekdays but may be enrolled later if admitted on the weekend and/or if person cannot consent during that time period (eg, if intubated). When a potentially eligible patient has been identified for the study (see screening criteria), the pneumonia hospitalisation registry (screening log) will be completed by staff trained to work on the study and then later the patient will be offered participation in the study.

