10.2. Screening/Enrolment Log

- The study screening log will be completed by site personnel and be forwarded to the sponsor or its representatives weekly for the required study monitoring and follow-up. The registry will include the following information as permitted by the Independent Ethics Committee (IEC) and may include:
 - Screening date;
 - Hospital site and ward;
 - Sex;
 - Nationality;
 - Surveillance area resident (yes/no);
 - Eligibility if not eligible, why;

- Consented (yes/no);
- Date of consent (day/month/year);
- If declined, reason not consented;
- Study participant ID;
- Date of admission to hospital (day/month/year);
- Year of birth;
- Pneumonia confirmed by Chest radiology (yes/no);
- ICU admission (yes/no);
- Samples collected.

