10.4. Visit 2 Day 30 (Final Diagnosis and Event Outcome)

The participant will be followed-up by telephone at 30 to 45 days after hospital admission. The date of the visit, the patient's final diagnosis and outcome for study-qualifying suspected CAP event will be recorded in the eCRF. If patient returns to study hospital for a standard - of care clinic visit for another reason, the visit may occur in person. RRIs will be collected if encountered during the collection of visit-related information or if the patient is contact by phone.

- The following data will be recorded in the study eCRF:
 - Any additional results from standard –of care pneumococcal and viral respiratory testing, including COVID-19 and RSV, that was not captured during Visit 1.
 - Additional information on hospitalisation data eCRF items not captured during Visit 1.
- Principal investigator (PI) or designee should make an outcome assessment of final diagnosis based on any information available over the hospitalisation of the patient. This may include both study and SOC exams, procedures and tests. This data point can be recorded on Day 30 or sooner if available. Final diagnosis categories will include:
 - CAP-radiologically confirmed;
 - CAP-not radiologically confirmed (eg, clinical CAP);
 - CAP-no chest radiology done; or
 - Other diagnosis (not CAP).
 - Acute Bronchitis.
 - Exacerbation of COPD.
 - Empyema/lung abscess.
 - Other Acute Lower Respiratory Infection. PFIZER CONFIDENTIAL CT45-GSOP-RF152.0 Low-Interventional Study Protocol Template 05-Dec-2019 Page 39 of 70

- Acute pulmonary exacerbation of congestive heart failure.
- Non-infectious process.
- Event disposition at 30 days after admission:
 - Fatal/deceased.
 - Not recovered/not resolved.
 - Recovered/resolved.
 - Recovered/resolved with sequelae.
 - Recovering/resolving.
 - Unknown.
- Vital Status (ie, deceased or living), including date and cause of death if deceased.
- RRIs per Section 16.2 and selected exposures and AEs related to Pfizer products per Section 16.3.

Case Definition for Radiologically Confirmed CAP

Patients in whom the treating physician clinically suspected pneumonia who meet the following 2 criteria will be considered to have radiologically confirmed CAP:

- 1. Has a radiologic finding that is consistent with pneumonia (eg, pleural effusion, increased pulmonary density due to infection, the presence of alveolar infiltrates [multilobar, lobar or segmental] containing air bronchograms); AND

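### The enrolled-versus-unenrolled check reads ICU status and radiological confirmation from different sources in the two groups, so differences in these two variables can appear or be hidden because of the source

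*SAP*

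**What the plan says.** SAP 6.3.1.1 compares age, sex, nationality, radiologically confirmed CAP and ICU status between "cases obtained from eCRF (enrolled patients) and Screening Log (not included in the eCRF/not enrolled) to evaluate the representativeness of the enrolled cases". For the tests it states: "We will perform chi-square or Fisher's exact test, as appropriate, for the categorical variable", with a t-test or rank test for continuous variables. It names no significance level for this check and no source or time window for individual variables.

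For enrolled patients, Protocol 10.3 has the eCRF record ICU stay and number of ICU days. Footnote e of the schedule of activities (Protocol 6) and Protocol 10.4 allow missing hospitalisation items to be added at the Day 30 visit. Radiological confirmation is a category of the final diagnosis, an "outcome assessment of final diagnosis based on any information available over the hospitalisation of the patient", recorded at Day 30 or sooner (Protocol 10.4).

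For unenrolled patients, the log fields in Protocol 10.2 include ICU admission as a yes/no and the item "Pneumonia confirmed by Chest radiology (yes/no"). Protocol 10.1.1 says that the log "will be completed by staff trained to work on the study and then later the patient will be offered participation", and Protocol 10.2 adds: "The study screening log will be completed by site personnel and be forwarded to the sponsor or its representatives weekly". Neither section sets a cut-off for the two items or requires them to be updated to discharge.

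The log is not confined to the unenrolled. It is the record "which will record all identified hospitalised patients admitted with pneumonia", enrolled or not (Protocol 10.1.1), and it carries the study participant ID (Protocol 10.2).

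**The concern.** The comparison is meant to show whether enrolled patients can stand in for those not enrolled. That matters because three incidence results lean on the enrolled. Sp+CAP and radiologically confirmed incidence multiply the CAP rate by proportions seen in study subjects (Protocol 12.4.2), and risk-group incidence applies enrolled proportions to unenrolled patients (SAP 6.3.4.1). Protocol 14 names differential enrolment by severity and age as a source of bias. ICU status is the only direct severity marker in the check, and it is one of the two variables read from different sources.

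If the log misses ICU stays that begin after the row was completed, the enrolled look sicker than the unenrolled when they are not. The same shortfall would conceal real under-enrolment of the severely ill. For radiology the direction is open: the eCRF item can draw on later imaging, but it may also be judged against a different definition.

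**Working it through.** **No planned figure to reproduce.** The documents give no ICU frequency and no log capture rate. The core of the point is textual; the arithmetic only shows how sensitive the test is.

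**The two sources side by side**

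| Variable | Enrolled (eCRF) | Unenrolled (log) |
|---|---|---|
| ICU | Stay and number of days; can be completed to Day 30 | Yes/no; no window |
| Radiology | Category of the investigator's final diagnosis, whole hospitalisation, Day 30 or sooner | Yes/no for chest radiology; no window |
| Age | Date of birth | Year of birth |
| Sex, nationality | Recorded directly | Recorded directly |

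Only the first two rows differ in a way that matters.

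**False signal, ICU**

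Assumptions: the same true ICU share p in both groups; the eCRF captures all stays; the log captures a fraction c; two-sided 5% level. Group sizes: 3,000 enrolled, a round number near the base-case total of about 3,063 in Protocol 12.1.2, and 70% enrolment, giving 3,000/0.70 − 3,000 = 1,286 unenrolled.

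The observed shares are p (enrolled) and cp (unenrolled). With d = p − cp, the chance of p<0.05 is approximately Φ[(d − 1.96·SE0)/SE1]. SE0 uses the pooled share and SE1 the separate shares.

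- p = 10%, c = 90%: observed 10% vs 9%; pooled 9.70%; SE0 = 0.00986; SE1 = 0.00968; (0.010 − 1.96×0.00986)/0.00968 = −0.96; Φ = 0.167.
- p = 10%, c = 80%: observed 10% vs 8%; pooled 9.40%; SE0 = 0.00973; SE1 = 0.00934; (0.020 − 1.96×0.00973)/0.00934 = 0.10; Φ = 0.540.

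For the full planned period, the protocol's inputs give 1,800 × 4 × 0.70 = 5,040 enrolled and 1,800 × 4 × 0.30 = 2,160 unenrolled. (Protocol 12.1.2 prints 5,400 enrolled; I use the product of its stated inputs.)

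| True ICU share | Capture | 3,000 vs 1,286 | 5,040 vs 2,160 |
|---|---|---|---|
| 5% | 90% | 10% | 14% |
| 5% | 80% | 29% | 45% |
| 10% | 90% | 17% | 26% |
| 10% | 80% | 54% | 77% |
| 15% | 90% | 24% | 38% |
| 15% | 80% | 74% | 93% |

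At 100% capture the rate is the nominal 5%.

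**Hidden difference, ICU**

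Suppose true shares of 10% enrolled and 14% unenrolled. With equal measurement, 3,000 vs 1,286 patients would detect this with about 96% power. The observed shares become equal when 0.14c = 0.10, that is c = 71%.

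**Radiology**

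If the same true state is read as 90% in the eCRF and 88% in the log, p<0.05 occurs about 50% of the time at 3,000 vs 1,286 and 71% at 5,040 vs 2,160. These shares are assumptions too.

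**The case against.** The strongest reply is that the log is not simply a snapshot at identification. CAP events are also added through monthly review of discharge codes (Protocol 12.1.3.5 and 12.4.2), when the whole stay is known. SAP 4.4 counts unenrolled patients only with a final diagnosis of CAP, although Protocol 10.2 lists no such field. Consent date and samples collected are filled in after identification. The Surveillance Manual, which is not among the documents, may fix the update rules. This stands: a reader might infer that every unenrolled value is frozen at screening, and the documents do not say so. Completion before participation is offered is only the default order. But mixed timing among unenrolled rows does not make them comparable with the eCRF.

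It follows that a plain log-to-log comparison could reverse the bias, because enrolled rows are prospective while unenrolled rows include some made after discharge. That is valid, and it is why the fix keeps the retrospective rows apart.

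A reader might also infer that confirmation in the enrolled always needs at least two signs or symptoms. The case definition in Protocol 10.4 requires them, but Protocol 11.3 defines radiological confirmation by the finding alone, and SAP 6.3.1.1 does not say which eCRF item it uses. The symptom count cannot carry the point; the difference in timing and type of judgement can.

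The source wording in SAP 6.3.1.1 could be read as merely labelling the two groups. Even so, it leaves the source of each variable unstated, and the plain reading is eCRF against log.

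Finally, the check contains neither pneumococcal status nor risk condition, so even a perfect version would not validate the Sp+CAP or risk-group proportions. Protocol 12.4.2 foresees stratified or imputation-based adjustment if log detail allows, and SAP 5.1 states that no decision rule applies. This limits the consequence; it does not make the two sources equivalent.

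**Conclusion.** The point holds in a limited form. ICU status and radiologically confirmed CAP are compared across sources that differ in time window and in kind of judgement, and nothing in either document aligns them. Differences in these two variables can appear or be hidden because of the source. It would go too far to say that they will: that depends on log capture, which is unknown, and at full capture there is no ICU artefact. Over the tabulated range (true ICU share 5% to 15%, capture 80% to 90%, the two sets of group sizes), the false-signal rate runs from about 10% to 93% against a nominal 5%. The percentages rest on those assumptions and on complete eCRF capture.

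The consequence is confined to one exploratory representativeness check, the only planned comparison of enrolled with unenrolled patients that I found. A reader might extend the concern to vaccine effectiveness, but that analysis uses enrolled patients only and does not draw on this comparison. The change is still worth making, because it is cheap and the check informs how three incidence results are read.

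**What to change.** In SAP 6.3.1.1:

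- Take ICU admission and chest-radiology confirmation from the screening log for both groups, linking enrolled rows by participant ID.
- Restrict the main comparison to prospectively identified log rows, and show rows added by retrospective discharge-code review separately.
- Report log-versus-eCRF agreement for both items among the enrolled. This also gives a direct estimate of log capture in that group.
- Keep the eCRF values for the enrolled as a separate descriptive column.

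The cost is a few sentences in the SAP and one linkage; the fields are already listed for the log. Protocol 10.2 lists no marker for retrospective rows, so the sites should confirm how these are identified. The downside is small: the log items are cruder than the eCRF items, which is the reason to keep the descriptive column.

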# 6.3.2. Exploratory Endpoint 2 – Differences in VE between PPV23 and PCV13

The difference in VEs of PCV13 and PPV23 against respective serotypes overall and among immunocompetent persons only.

## 6.3.2.1. Exploratory Endpoint 2 - Main Analysis

In this analysis, the VE of PCV13 against VT (PCV13) pneumococcal CAP will be obtained from the primary analysis as described in Section 6.1.1.1. The same method will be used to estimate the VE of PPV23 against VT (PPV23) pneumococcal CAP. The crude difference will then be calculated as:

VE of PCV13 against VT (PCV13) pneumococcal CAP – VE of PPV23 against VT (PPV23) pneumococcal CAP

To evaluate the differences of the effectiveness of these two vaccines, the ORs from both the models that used conditional logistic regression using the propensity matching cases and controls, will be tested using the likelihood ratio and/or z-score test as described in Appendix 3.4.

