## 6.1.1.1. Primary Endpoint 1- Main Analysis

## Pneumococcal Vaccination Status for Primary Endpoint

Pneumococcal vaccination status is defined as receipt of ≥1 dose of PCV13 or PPV23 and confirmed by electronic registries. Vaccination status will be categorized as: a) never exposed, b) ever exposed. Ever exposed will be subdivided into: i) exposed <5 years, and ii) exposed ≥5 and <10 years. Persons vaccinated ≥10 years will be considered unexposed.

The Madrid vaccination guidelines (Protocol Table 1) stipulate the timing of PCV13, and we will exclude following participants from the VE analyses:

- Immunocompetent participants who received PCV13 within one year after receiving PPV23
- Immunocompromising participants who received PCV13 within eight weeks after receiving PPV23
- Any participants who received PCV20

Note: Cases and controls include either radiologically confirmed CAP, not radiologically confirmed, or chest radiology not done. If more than 5% of the CAP cases are not radiologically confirmed, then a separate analysis will be performed selecting cases and controls only from the radiologically confirmed CAP cases.

The characteristics of cases and controls will be compared using the chi-square test.

DMB02-GSOP-RF02 5.0 Statistical Analysis Plan Template 05-Dec-2019
PFIZER CONFIDENTIAL
Page 31
TMF Doc ID: 98.03

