For the primary endpoint, the cases will be the patients with CAP in whom PCV13 serotypes are identified by any method and the controls will be the patients with CAP without having VT serotype (even the CAPs for which the serotype was not identified). Multivariable logistic regression model (Appendix 3.3), will be applied to estimate odds of exposure to PCV13 among cases versus controls. All VE estimates will be calculated as  $(1 - \text{odds ratio}) \times 100\%$ . Both unadjusted and adjusted VE will be estimated. Patients' age, sex, study site and the variables deemed to be potential confounders on the basis of prior knowledge (e.g. nationality to be modeled as Spanish vs. non-Spanish; risk level to be modeled as low vs. at-risk vs. high-risk; BMI category to be modeled as obese vs. overweight vs. normal vs. underweight; PSI score as continuous; current drug abuse; antibiotic use within past 14 days; influenza vaccination within the last year; pneumonia in last year [ordinal variable, 0,1,2,3] and PPV23 receipt in past 5 years) will be included in the multivariable regression model for adjustment. Initially, we will employ bivariate models, and only the variables significant at p<.20 in the bivariate models will be included in the final model for adjustment.

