#### Selection of controls using propensity score matching

In the 1st sensitivity analysis, the cases will be the patients with CAP in whom PCV13 serotypes are identified by any method and the controls will be the patients with CAP without having VT serotype (even the CAPs for which the serotype was not identified). The controls will be selected using propensity score matching. A propensity score is the conditional probability of assignment to a treatment given a vector of covariates including the values of all treatment confounders (vida infra). We will select the required number of controls matching by the propensity score of the case. Several types of propensity score matching are available in literature. We will use nearest neighbor matching (without replacement, meaning a control cannot be the control of any other case) within a specified caliper distance (Rosenbaum & Rubin, 1985). The caliper distance will be set to 0.2 of propensity score (i.e., 0.2 standard deviations of whatever distance will be measured), so that matching controls remain within the specified distance of the propensity score. Note that 0.2 of the pooled standard deviation of the logit of the propensity score will eliminate approximately 99% of the bias due to the measured confounders (Austin 2011). The maximum number of controls for a case will be determined based on the exact case-control ratio in the data. If less than the maximum number of controls exists within the set caliper distance of 0.2, then only those controls within the caliper distance will be selected and that case will have less than the maximum number of controls.

DMB02-GSOP-RF02 5.0 Statistical Analysis Plan Template 05-Dec-2019
PFIZER CONFIDENTIAL
Page 32
TMF Doc ID: 98.03

We may also perform a sensitivity analysis by selecting controls setting the caliper distance to 0.1 of the propensity score.

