## Variables to be used to calculate the propensity scores

Variables for calculating the propensity score.

- Patients' age: continuous
- Sex: female=0, male=1
- Nationality: Spanish=0, non-Spanish=1
- Risk level: low-risk=0, at-risk=1, high-risk=2
- PSI score: continuous
- Antibiotic use within past 14 days: no=0, yes=1)
- Influenza vaccination within past one year: yes=0, no=1
- Pneumonia in the last year: ordinal value=0, 1,2,3
- Season of admission: Spring (Mar-May)=0, Summer (Jun-Aug)=1, Autumn (sep-Nov)=2, Winter (Dec-Feb)=3.
- PPV23 receipt in past 5 years: yes=0, no=1
- CAP event occurrence during COVID-19 pandemic: 0=not during COVID-19, 1=During COVID-19 (The study is started in the pandemic period; the variable will be used if we find a non-pandemic period during the study period)

The study site will be exactly matched. Note that the categorical variable will be put in the model like the ordinal values.

The conditional logistic regression will be employed to estimate odds of exposure to PCV13 among these matched cases and controls. The VE estimate will be calculated as  $(1 - \text{odds ratio}) \times 100\%$ . We will use a two-sided alpha of 0.05 for all analyses.

In the 2nd sensitivity analysis (PPV23 Naïve population), the cases will be the hospitalized CAP in whom PCV13 serotypes are identified by any method and had not received PPV23 in the last five years from the date of visit; the controls (also PPV23 Naïve population), will be selected using the propensity score matching as described above. A conditional logistic regression will be employed to estimate odds of exposure to PCV13 among cases versus controls in the PPV23 naïve population. The VE estimate will be calculated as (1 – odds ratio) × 100%. We will use a two-sided alpha of 0.05 for all analyses.

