#### Appendix 3.3. Calculation of odds ratio

To measure the effectiveness of the PCV13 and PPV23 against the target outcomes, the multivariable logistic regression model will be used Coefficient of the vaccine variable in the model will be exponentiated to estimate the odds ratio. To address the effect of the confounding

DMB02-GSOP-RF02 5.0 Statistical Analysis Plan Template 05-Dec-2019 PFIZER CONFIDENTIAL Page 55 TMF Doc ID: 98.03 variables, the variables that were independently associated with the outcome at p<0.10 in a bivariate analysis will be selected. When selecting the covariates for the final model, the rule of 10 events per covariate (Peduzzi et al 1996) will be followed. The vaccine effectiveness (VE) will be calculated as

VE = 1- adjusted odds ratio  $\times$  100.

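### PPV23 effectiveness is adjusted and matched on recent PPV23 receipt, which is part of its own exposure; depending on how exposure and score are coded, the estimate can reduce to the 5-<10 year effect

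*SAP*

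**What the plan says.** SAP 6.3.2.1 takes PCV13 effectiveness from the primary analysis in SAP 6.1.1.1 and then states: "The same method will be used to estimate the VE of PPV23 against VT (PPV23) pneumococcal CAP". For the test of the difference it uses "the ORs from both the models that used conditional logistic regression using the propensity matching cases and controls".

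The method carried over has these parts:

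- **Exposure (SAP 6.1.1.1).** Vaccination status is defined for either vaccine. Ever exposed is split into "i) exposed <5 years, and ii) exposed ≥5 and <10 years", and vaccination ten or more years ago counts as unexposed.
- **Regression covariates (SAP 6.1.1.1).** The list of examples ends with "PPV23 receipt in past 5 years) will be included in the multivariable regression model for adjustment". A screen follows: "only the variables significant at p<.20 in the bivariate models will be included in the final model". Appendix 3.3, which gives one recipe for both vaccines, has a different cut-off: "the variables that were independently associated with the outcome at p<0.10 in a bivariate analysis will be selected".
- **Propensity score (SAP 6.1.1.2).** It is defined thus: "A propensity score is the conditional probability of assignment to a treatment given a vector of covariates". The variable list includes "PPV23 receipt in past 5 years: yes=0, no=1". No screen is stated for this list. The section opens by saying that the sensitivity analyses cover PPV23 as well as PCV13.

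No section of the SAP or protocol drops the recent-PPV23 item when PPV23 is the exposure.

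**The concern.** For PCV13 effectiveness, recent PPV23 receipt is a sensible covariate. For PPV23 effectiveness it is the same variable as the under-5-year exposure level. Adjusting for it, or matching on it, can remove recent recipients from the comparison that the PPV23 term is meant to measure.

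SAP 3.3.1 defines exploratory endpoint 2 as the difference between the final adjusted effectiveness of the two vaccines. If the item stays in, that difference can set PCV13 given at any time under 10 years against PPV23 given 5-<10 years ago. A single-term regression would fit normally and give no warning.

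**Working it through.** **Plan's own figure.** The documents give no figure for PPV23 effectiveness or for the comparison. The only stated calculation is the PCV13 base case in Protocol Table 6 and SAP 2.2. With 15% coverage in controls and VE 60%, exposure in cases is 0.15×0.4/(0.85+0.15×0.4) = 0.0659. Fleiss with continuity correction, two-sided alpha 0.025, 80% power and ratio 1,692/170 gives 170 cases and 1,692 controls, as stated. These counts are borrowed below.

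**1. Single exposure term.** Let E = 1 for PPV23 under 10 years and R = 1 for PPV23 under 5 years. The model is logit = a + bE + cR.
- unexposed: a
- 5-<10 y: a + b
- <5 y: a + b + c

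Three cells and three parameters, so b is exactly the 5-<10 y log odds ratio.

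**2. Two exposure levels.** The columns are intercept, <5 y, 5-<10 y and R. R equals the <5 y column, so the rank is 3 of 4. The two identical columns cannot be separated, but their sum can be estimated. With true VE of 50% (<5 y) and 20% (5-<10 y), the fit returns 50% and 20%.

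**3. Size in the single-term model.** If s is the share of exposed controls vaccinated under 5 years ago, the ordinary under-10-year odds ratio is s×OR(<5 y) + (1−s)×OR(5-<10 y). The understatement is therefore s×[VE(<5 y) − VE(5-<10 y)]. VE by band is assumed. With 50%/20%:
- s = 9%: 0.09×0.50 + 0.91×0.80 = 0.773, VE 22.7%; with the item, 20.0%
- s = 31%: 0.31×0.50 + 0.69×0.80 = 0.707, VE 29.3%; with the item, 20.0%

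**4. Plausible s.** Protocol Table 1 schedules PPV23 from January 2018 only for high-risk persons. Assume on-schedule vaccination at a constant yearly rate. For other persons admitted at time t, the recent window is 2023−t (zero from January 2023) and the under-10-year window is 2028−t. At the March 2021 start (t = 2021.2) s = 1.8/6.8 = 26%. Over admissions to mid-2024:
- recent: 1.8²/2 = 1.62
- under 10 years: (6.8² − 3.5²)/2 = 17.0
- s = 1.62/17.0 = 9.5%

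Ending in late 2024 or Q1 2025 gives 9.1% or 8.4%. For high-risk persons (36% of admissions, Protocol 12.1.2), 5 of 10 years are recent. Dividing by the 3.3 admission years, the average windows for the others are 0.49 and 5.15 years, so the overall share is (0.36×5 + 0.64×0.49)/(0.36×10 + 0.64×5.15) = 2.11/6.90 = 31%. This also assumes the same yearly PPV23 rate in both groups.

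| Assumed VE (<5 y / 5-<10 y) | s = 8.4-9.5% | s = 31% |
|---|---|---|
| 50% / 20% | 2.5-2.9 points low | 9.3 |
| 30% / 10% or 40% / 20% | 1.7-1.9 | 6.2 |
| no waning | 0 | 0 |

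**5. Precision without waning.** Woolf standard errors, VE 40% in both bands, 170 cases and 1,692 controls:
- coverage 46.7% (PPV23 uptake in Protocol Table 2 weighted by cohort size): 0.169 rises to 0.174 (s = 9%) or 0.191 (s = 31%)
- coverage 25% (assumed): 0.213 rises to 0.222 or 0.250

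**6. The screen.** At 46.7% coverage, across the assumed effects, the item is kept with probability 0.25-0.46 at p<.20 and 0.14-0.31 at p<0.10 when s = 9%. When s = 31% the figures are 0.38-0.81 and 0.25-0.70. It is kept more often when recent PPV23 works better.

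**7. Matched models.** If the score models PPV23 receipt, recent recipients are all exposed, so the item predicts exposure perfectly. They match only each other, and those sets carry no information. In a simulation with one other covariate, 20% of subjects vaccinated under 5 years and 25% at 5-<10 years ago, and VE 50%/10%, the pooled value is 1 − (20×0.5 + 25×0.9)/45 = 27.8%.

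| Score models | VE returned (50%/10%) | VE returned (40%/40%) | Sets mixing recent and other subjects |
|---|---|---|---|
| PPV23 receipt | 8.5% | 40.2% | 0% |
| PCV13 receipt | 10.3% | 32.5% | 5-6% |
| case status | 12.1% | 33.8% | 6-14% |

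**The case against.** The strongest case against has five parts.

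- **The exposure levels.** A reader might infer that the recent PPV23 effect cannot be estimated at all. The documents do not support that. With the two levels in SAP 6.1.1.1, dropping the redundant column restores recent-versus-unexposed with nothing lost, and the redundancy shows on first fit. This stands. Only a collapsed exposure term biases the regression.
- **The screen.** A reader might also infer that the regression always gives the 5-<10 year effect. It does not: at a 9% share the item is more likely to be dropped than kept, and PPV23 effectiveness is then the ordinary under-10-year estimate. This stands for the regression. It does not reach the propensity list, which feeds the test of the difference.
- **Intent.** The regression list is introduced as examples of potential confounders, and the matched analyses name PCV13 as the exposure. The authors may have meant vaccine-specific lists. That is plausible, but SAP 6.3.2.1 carries the method over without saying so, and SAP 6.1.1.2 extends the matched analyses to PPV23.
- **The score.** The exact matched result needs a score for PPV23 receipt. With a score for PCV13 receipt or case status, some sets mix recent and other subjects, and more would with the full covariate list. The result is then only approximate.
- **Size.** Effectiveness, waning and timing are all assumed. With 170 cases, 1,692 controls and 46.7% coverage, a VE of 22.7% has a 95% interval of about −7% to 44%, so 2-3 points is small beside sampling error. The endpoint is exploratory, and SAP 5.1 states no decision rule.

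**Conclusion.** The point holds in conditional form. As written, the plan conditions PPV23 effectiveness on part of PPV23 exposure.

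- **Regression:** with a single under-10-year term and the item retained, the estimate is exactly the 5-<10 year effect. With two levels, the item is redundant and harmless once dropped.
- **Matched models:** the odds ratio is the 5-<10 year effect if the score models PPV23 receipt, and approximately so otherwise.

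If PPV23 protection wanes, PPV23 effectiveness is too low and the PCV13-minus-PPV23 difference too high by the same number of points. That is about 2-3 points in immunocompetent persons and possibly 6-9 overall. These sizes rest on assumed waning, on-schedule vaccination at a constant rate and, for the overall figure, an assumed recent share of about 31%.

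Without waning there is no bias in the regression, or in matching on a PPV23-receipt score; only the standard error grows. The lower values in the simulation under the other two scores come from a model with one other covariate, and no weight is placed on them.

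A reader might infer that the primary result is affected. It is not, because the item is a proper covariate for PCV13. The reach is exploratory endpoint 2 and the PPV23 sensitivity analyses (SAP 6.1.1.2, Protocol 12.1.1).

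**What to change.** State in SAP 6.3.2.1 and in SAP 6.1.1.2 that, when PPV23 is the exposure, the item for PPV23 receipt within five years is removed from both the regression covariates and the propensity-score variables.

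The cost is one sentence in each of two sections, with no new data. Time since PPV23 stays in the analysis through the exposure levels of SAP 6.1.1.1, so nothing is lost.
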